Scheduled post-operative assessments following the initial assessment will include a 3 month, 6 month, and one year follow up appointment. Evaluation at the 3-month and 6-month follow-up appointment, will include photos of the surgical site, evaluation of the skin graft and any areas of necrosis or tendon exposure, survey of presence of pain and paresthesia, and the QuickDASH survey. During the 1 year follow-up, in addition the assessments described above, the Vancouver Scale Assessment will be performed by a Co-Investigator who is blinded. Areas of tendon exposure will be treated with xeroform dressing changes.

During surgery and at the scheduled follow up all subjects will have standardized photographs taken utilizing a custom backdrop and a centimeter scale. These pictures will be used to assess wound size and dimension at each encounter, including the original surgery. This will allow us to measure the rate of wound healing, contracture, and rate of skin graft necrosis. The pictures will be analyzed with the SigmaScan planimetry program. This protocol has been previously validated and published.[15]

Subjects will be evaluated by the occupational therapy team prior to their surgery in the pre-operative holding area and during their admission to the hospital. They will be assessed using standard measurement from a goniometer and dynamometer and also given instructions for wrist range of motion exercises. During follow up, subjects will be referred to occupational and physical therapy at the discretion of the attending physician.

Subjects removed from study for unacceptable adverse events will be followed until resolution or stabilization of the adverse event.

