13.0 Statistical Considerations

Endpoints:

1. Rate of tendon exposure. Previously reported from 12-55%. [7, 16-19]
2. Rate and percent of skin graft necrosis. Rate previously reported to be from 7%-51%. [7, 9, 16, 20-22]
Percentage of skin graft loss ranges from $\leq 5\%$ - $\geq 20\%$. [9, 16]
3. Rate of paresthesia. Previously reported to be 36%- 50%. [9, 20]
4. Aesthetic outcome of donor site on Vancouver Scar Scale, a validated objective assessment of scar appearance. [23] Previous scores are reported to be 4.7/13 without Integra and 4.2/13 with Integra. [14, 24]
In particular, we will be focusing on the pliability aspect of the Vancouver Scar Scale, which will be a measure of the functionality of the skin overlying the donor site. The scores will be taken at the 3,6, and 12 month follow up.
5. The Disabilities of the Arm, Shoulder and Hand (DASH) outcome measure is a 30 question survey used to quantify the symptoms and function of any person with musculoskeletal disorders of the upper limb. It is used to determine the impact that a particular disorder has on an individual's life. [25, 26] The QuickDASH is a shortened version of the DASH that has been validated to be as significant as the full questionnaire. [27] While the QuickDash scores of RFFF subjects have not been reported, previous DASH scores have been reported to be 6.93 ± 5.54 in RFFF subjects compared to 2.95 ± 4.42 in non-RFFF subjects. [28]
6. Differences in range of motion at the hand, previously reported to be 22-27 degrees difference [8]
7. Differences in grip and pinch strength in the donor site hand, previously reported to be about a 7kg difference in pinch strength and a 0.75kg difference in grip strength. [29]
8. Wound contracture and Skin Pliability. Normal results are reported below.

Statistical Analysis:

We plan to enroll 50 subjects in each group. All hypothesis testing will two sided and performed at the 0.05 significance level. All analysis will be performed in SAS Version 9.4 (Cary, NC). No interim monitoring is planned for this study.

The analysis and estimated power for each endpoint is described below.

1. Rate of tendon exposure
 - a. We expect about a 25% rate of tendon exposure in the group that does not use Integra, while in the Integra group we hope to have a rate of tendon exposure of below 5%. We will test this hypothesis using a chi-squared test of equal proportions. We will have 81% power to detect this difference with 50 subjects in each group.

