 - a. Range of motion will be measured by resident physicians taking part in the project who will be trained by the occupational therapy team at our institution. The measurements will be taken using electric goniometers so as to standardize the measurements as much as possible.
 - i. Previously reported differences in pre and postoperative range of motion of wrist flexion and extension have ranged from non-statistically significant to about 27 degrees and 22 degrees, respectively.¹
 1. We will expect the difference in wrist flexion and extension in the non-Integra group to be 25 degrees and 20 degrees, respectively.
 2. We will expect the difference in flexion and extension in the Integra group to be 15 and 10 degrees, respectively.[8]
 3. We will again employ two sample t-tests (or Wilcoxon Rank Sum Tests) to test for differences in these angle measurements. Assuming a common standard deviation of five degrees, we will have 99% power to detect a difference in five degrees using a two sample t test.
 - b. Hand strength will be measured by pinch and grip strength dynamometers obtained from the occupational therapy department at our institution. These measurements will be taken at 3 month, 6 month, and 1 year follow up clinic visits.
 - i. Grip strength has been reported to be about a 7kg difference between pre-operative and post-operative measurements, while Pinch strength has been shown to differ by approximately 0.75kg. [29]
 - ii. For the non-integra group, we predict a difference in grip strength of approximately 5kg, while the pinch strength will differ but about 0.75kg
 - iii. For the Integra group, we predict that the difference in grip strength will be approximately 3kg while the pinch strength will differ by approximately 0.25kg.
 - iv. At each time point, we will compare the hand strengths of the Integra and non-Integra groups using two sample t-tests or Wilcoxon Rank Sum Tests as appropriate. Assuming a 5kg grip strength standard deviation in each group, we will have over 99% power to detect differences of 5kg and 7 kg in each group.

The Use of Integra® in Coverage of Radial Forearm Free Flap Donor Site Defect

Comprehensive Cancer Center of Wake Forest University (CCCFWU)

CCCFWU # 99915A

- v. For pinch strength, we assume both groups have a standard deviation of 1kg. To detect a difference 0.75kg, we will have 95% power using a two sample t-test.

7. Wound Contracture and Skin Pliability

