- a. We will use the same planimetry software to determine the percent of wound contracture.
 - i. Utilizing a dermal substitute, wound contracture has been shown to be as low as 15% of total area. We will expect the same amount from our study. [30]
 - ii. Wound contracture utilizing standard STSG has been shown in animal models to cause wound contracture of up to 38-41%. We will expect wound contracture of about 30% from our study. [31,32]
- b. Skin Pliability
 - i. We plan to use a Cutometer MPA 580 for measurements of skin pliability. We currently have this device on our budget for next year awaiting approval and are separately applying for a Plastic Surgery Foundation grant to fund these measurements.
 - ii. We plan to measure Pliability (Ua), Elasticity (Ue), Retraction (Ur), Viscoelasticity (Uv), and Extension (Uf)
 - 1. Previously measured values for these parameters in reconstruction utilizing Integra are as follows. [33]
 - a. $Ua = 0.083$ (0.192 Control)
 - b. $Ue = 0.088$ (0.153 Control)
 - c. $Ur = 0.037$ (0.086 Control)
 - d. $Uv = 0.039$ (0.068 Control)
 - e. $Uf = 0.098$ (0.221 Control)
 - f. Ur/Uf (Gross Elasticity) = 0.377
 - g. Ur/Ue (Elastic Function) = 0.125
 - h. Ua/Uf (Biological Elasticity) = 0.846
 - 2. Previously measured values for these parameters in STSG are reported as ratios and are listed here. [34]
 - a. Ur/Uf (Gross Elasticity) = 0.553
 - b. Ur/Ue (Elastic Function) = 0.818
 - c. Ua/Uf (Biological Elasticity) = 0.881
 - 3. For our study, we will expect the following parameters
 - a. Integra+STSG
 - i. $Ur/Uf = 0.4$
 - ii. $Ur/Ue = 0.1$
 - iii. $Ua/Uf = 0.8$
 - b. STSG
 - i. $Ur/Uf = 0.6$
 - ii. $Ur/Ue = 0.8$
 - iii. $Ua/Uf = 0.9$
 - iii. Should we not obtain funding for a cutometer, we will obtain measurements of maximal skin distension over the grafted area and compare it in a ratio to the maximal skin distension over the same area in the opposite arm.

The Use of Integra® in Coverage of Radial Forearm Free Flap Donor Site Defect

Comprehensive Cancer Center of Wake Forest University (CCCFWU)

CCCFWU # 99915A

1. In this manner, we would expect the Integra and STSG to give a ratio of about 0.75, while the STSG would give a ratio of about 0.4

References

1. Yang, G.F., et al., Forearm free skin flap transplantation: a report of 56 cases. 1981. *Br J Plast Surg*, 1997. 50(3): p. 162-5.

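### Wrist motion is compared on pre-to-post differences with no adjustment for the pre-operative angle, and Section 13.0 prespecifies no covariate in any comparison

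*Combined protocol and SAP*

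**What the plan says.** Wrist motion is covered in two places. Section 5.0 has the occupational therapy team assess subjects in the pre-operative holding area, and again during admission, with a goniometer and a dynamometer. Section 13.0, item 6a, expects pre-to-post differences in flexion and extension of 25 and 20 degrees without Integra, and 15 and 10 degrees with it. It then states: "We will again employ two sample t-tests (or Wilcoxon Rank Sum Tests) to test for differences in these angle measurements". The power statement assumes a common SD of five degrees and claims 99% power for a five-degree difference. On sample size, Section 13.0 says: "We plan to enroll 50 subjects in each group".

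Wound area is covered in Section 5.0: "During surgery and at the scheduled follow up all subjects will have standardized photographs taken utilizing a custom backdrop and a centimeter scale". It continues: "These pictures will be used to assess wound size and dimension at each encounter, including the original surgery". The stated purpose follows: "This will allow us to measure the rate of wound healing, contracture, and rate of skin graft necrosis". In Section 13.0, item 7a says: "We will use the same planimetry software to determine the percent of wound contracture". It expects 15% contracture with a dermal substitute and about 30% with a standard graft, and it names no test, SD or power.

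Scar scale, QuickDASH, motion and strength are all assigned two-sample t or Wilcoxon tests, and the yes/no endpoints chi-squared tests. No covariate, stratification factor or regression model appears in Section 13.0.

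**The concern.** A pre-operative angle is the standard covariate for a follow-up angle. Subtracting it amounts to assuming a slope of exactly one between the two readings. When the correlation is below one, subtraction carries the measurement error of the first reading into the outcome. It also over-corrects for chance baseline differences: the arm that happens to start with more motion will appear to lose more. A model that estimates the slope avoids both problems and needs no new data.

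Wound area at surgery raises a similar question, since it could also explain some of the variation in motion, scar and function. What is at stake is precision: wider intervals than the collected data may allow.

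**Working it through.** **Inputs.** From Section 13.0: 50 per arm, two-sided 0.05, motion SD 5 degrees, difference 5 degrees. The SD is read as that of the pre-to-post difference, because the sentence refers back to those differences. The pre-post correlation and the correlation of wound area with any outcome are not in the documents, so every r below is an assumption.

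**The plan's own figure.** The standard error of the difference between arms is 5 × √(2/50) = 1.00 degree, so the noncentrality is 5/1.00 = 5. With 98 degrees of freedom, power is 99.9%, which agrees with the stated 99%. The 95% half-width is 1.96 × 1.00 = 1.96 degrees.

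**Adjusting for the pre-operative angle instead of subtracting it.** With equal pre and post variances σ²:
- change-score variance = 2σ²(1−r)
- variance after adjustment = σ²(1−r²)
- ratio = (1−r²)/(2(1−r)) = (1+r)/2

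Applied to the plan's SD and n, the half-width is 1.96 × √ratio and the equivalent number per arm is 50/ratio:
- r = 0.3: ratio 0.65; half-width 1.58 degrees; equivalent to 50/0.65 ≈ 77 per arm
- r = 0.5: ratio 0.75; half-width 1.70 degrees; equivalent to 50/0.75 ≈ 67 per arm
- r = 0.7: ratio 0.85; half-width 1.81 degrees; equivalent to 50/0.85 ≈ 59 per arm

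**If the variances differ.** Let the pre and post SDs be σ₀ and σ₁. Change-score variance minus adjusted variance is (σ₀² + σ₁² − 2rσ₀σ₁) − σ₁²(1−r²) = (σ₀ − rσ₁)², which is never negative. Equal variances therefore set the size of the gain, not its direction. The cost is one degree of freedom (97 instead of 98).

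**If item 6a instead means raw follow-up angles.** The ratio is then 1−r²: 0.91, 0.75 and 0.51 at r = 0.3, 0.5 and 0.7. The adjusted model is again the more precise.

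**Chance baseline imbalance.** The between-arm difference in mean pre-operative angle has a standard error of √(2/50) = 0.2 SD. An imbalance of that size shifts the change-score comparison by (1−r) × 0.2 SD, or 0.14, 0.10 and 0.06 SD at r = 0.3, 0.5 and 0.7. With σ = 5/√(2(1−r)) = 4.23, 5.00 and 6.45 degrees, that is about 0.59, 0.50 and 0.39 degrees.

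**Wound area as a covariate.** Residual variance falls by r² and the standard error is multiplied by √(1−r²):
- r = 0: 0% and 1.000
- r = 0.1: 1% and 0.995
- r = 0.3: 9% and 0.954
- r = 0.5: 25% and 0.866

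At r = 0.1, 0.3 and 0.5 the half-widths change as follows:
- motion: from 1.96 to 1.95, 1.87 and 1.70 degrees
- scar score (SD 1): from 0.392 to 0.390, 0.374 and 0.339
- QuickDASH (SD 10): from 3.92 to 3.90, 3.74 and 3.39

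For motion these figures start from the unadjusted test. Once the pre-operative angle is in the model, r must be read as the correlation that remains.

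**The case against.** The strongest reply is that nothing is broken. The unadjusted tests are valid in a randomised trial, their error rate already allows for chance imbalance, and power for motion, scar and QuickDASH exceeds 99% at the plan's own effects. All of that stands. It does not remove the gain in precision for motion, where the covariate precedes surgery and the adjusted variance cannot exceed the change-score variance beyond the cost of one degree of freedom.

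The objections to using wound area carry more weight. A reader might infer that the area at surgery goes unused. The documents do not support that: it is collected to measure healing, contracture and necrosis, and a percent contracture needs it as its reference. A reader might also infer that item 7a has an unadjusted test to replace, but it names none. Nor do the documents show that precision is being lost on scar or function. They give no correlation of area with any outcome and no range of flap sizes, and at r = 0 the gain is nil.

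Timing matters as well. Section 4.0 randomises at registration, before treatment, so area is a post-randomisation measurement. Section 5.0 places the photograph during surgery without saying whether it precedes grafting. Only the one-year scar assessor is said to be blinded. If knowledge of the arm could influence the defect, adjusting for its area could introduce bias. This rules wound area out as a covariate in the main analysis.

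**Conclusion.** The point holds for wrist motion, as a matter of efficiency. Section 13.0 prespecifies no covariate, and the pre-operative angle, measured before surgery, is used only by subtraction. Adjusting for it multiplies the variance by 0.65 to 0.85 over assumed correlations of 0.3 to 0.7, and the half-width falls from 1.96 to between 1.58 and 1.81 degrees. These sizes rest on equal pre and post variances and on reading the plan's SD as that of the difference. The benefit is narrower intervals and removal of a baseline-imbalance shift of roughly half a degree. It is not a rescue of power, and no figure in the plan is wrong on this account.

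For wound area, the supported statement is narrower. It is the implied denominator of percent contracture and never a covariate. Any gain from adjusting for it runs from nothing to 25% of residual variance at an assumed r of 0.5, and depends on conditions that the documents do not establish.

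**What to change.** In Section 13.0, item 6a, specify that wrist flexion and extension are each analysed in a linear model with the follow-up angle as outcome and with arm and pre-operative angle as explanatory variables. Report the adjusted difference with its 95% interval, and show the planned unadjusted t or Wilcoxon result alongside. Name the follow-up visit: item 6a gives none, and goniometry is not in Section 5.0's list of follow-up assessments.

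Optionally, add a sensitivity analysis of scar score, QuickDASH and motion that also includes wound area at surgery. State two conditions for it: the area is recorded before coverage is applied, and defect size does not depend on the assigned arm. If either cannot be confirmed, leave it out.

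The cost is a few lines of SAP text, written before any outcome data by arm are seen so that the covariate is not chosen after the fact. No new measurement, visit or subject is needed if motion is measured at follow-up as item 6a intends.

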6.0 Data Management

Race Verification Form	ORIS
Protocol registration form	ORIS
Survey Data Capture	REDCap
PHI Data Capture	REDCap

The Use of Integra® in Coverage of Radial Forearm Free Flap Donor Site Defect

Comprehensive Cancer Center of Wake Forest University (CCCFWU)

CCCFWU # 99915A

13.0 Statistical Considerations

Endpoints:

1. Rate of tendon exposure. Previously reported from 12-55%. [7, 16-19]
2. Rate and percent of skin graft necrosis. Rate previously reported to be from 7%-51%. [7, 9, 16, 20-22]
Percentage of skin graft loss ranges from $\leq 5\%$ - $\geq 20\%$. [9, 16]
3. Rate of paresthesia. Previously reported to be 36%- 50%. [9, 20]
4. Aesthetic outcome of donor site on Vancouver Scar Scale, a validated objective assessment of scar appearance. [23] Previous scores are reported to be 4.7/13 without Integra and 4.2/13 with Integra. [14, 24]
In particular, we will be focusing on the pliability aspect of the Vancouver Scar Scale, which will be a measure of the functionality of the skin overlying the donor site. The scores will be taken at the 3,6, and 12 month follow up.
5. The Disabilities of the Arm, Shoulder and Hand (DASH) outcome measure is a 30 question survey used to quantify the symptoms and function of any person with musculoskeletal disorders of the upper limb. It is used to determine the impact that a particular disorder has on an individual's life. [25, 26] The QuickDASH is a shortened version of the DASH that has been validated to be as significant as the full questionnaire. [27] While the QuickDash scores of RFFF subjects have not been reported, previous DASH scores have been reported to be 6.93 ± 5.54 in RFFF subjects compared to 2.95 ± 4.42 in non-RFFF subjects. [28]
6. Differences in range of motion at the hand, previously reported to be 22-27 degrees difference [8]
7. Differences in grip and pinch strength in the donor site hand, previously reported to be about a 7kg difference in pinch strength and a 0.75kg difference in grip strength. [29]
8. Wound contracture and Skin Pliability. Normal results are reported below.

Statistical Analysis:

We plan to enroll 50 subjects in each group. All hypothesis testing will two sided and performed at the 0.05 significance level. All analysis will be performed in SAS Version 9.4 (Cary, NC). No interim monitoring is planned for this study.

The analysis and estimated power for each endpoint is described below.

1. Rate of tendon exposure
 - a. We expect about a 25% rate of tendon exposure in the group that does not use Integra, while in the Integra group we hope to have a rate of tendon exposure of below 5%. We will test this hypothesis using a chi-squared test of equal proportions. We will have 81% power to detect this difference with 50 subjects in each group.
2. Rate and percent of skin graft necrosis
 - a. We expect about a 20% rate of skin graft necrosis in the STSG group and about a less than 5% rate of skin graft necrosis in the Integra group. To test for a significant difference in the STSG and STSG with Integra groups, we will employ a chi-squared test of equal proportions. We will have 62% power to detect the difference between the two groups.

The Use of Integra[®] in Coverage of Radial Forearm Free Flap Donor Site Defect

Comprehensive Cancer Center of Wake Forest University (CCCFWU)

CCCFWU # 99915A

- b. In the STSG group, we expect about 10% of the graft to become necrotic, while we believe that below 5% of the STSG with Integra group to become necrotic. We will have approximately 16% power to detect this difference using a chi-squared test.
 - c. While the study may be underpowered to make this particular observation statistically significant, this parameter is not a primary objective of the study but will be easy to measure.
 3. Presence of pain and paresthesia and severity on a 1-10 scale
 - a. In the split thickness skin graft group, we expect about 20% of the subjects to still have pain at the radial forearm site, while about 35% of these subjects will have significant paresthesias. In the Integra group, we expect about 10% of the subjects to have pain at the radial forearm site, while about 20% of these subjects will likely have paresthesias. To test for significant difference in the two groups, we will again employ a chi-squared test. We will have 29% power to detect a significant difference in pain at the radial forearm site and 39% power to detect a significant difference in the rates of paresthesias.
 - b. Of the subjects that have pain we expect those who have had Integra[®] placed to have pain at a level of an average of about 3, while those who have not had Integra[®] will have pain at an average level of 7. After evaluating the distribution of the scaled scores, we will test if these means are equal using a t-test if data appear normal and a Wilcoxon Rank sum test if not. Assuming the two groups share a common standard deviation of 3, we will have over 99% power to detect this difference using a t-test. If data appears non-normal, assuming the probability that an observation in the Integra[®] group has lower severity of pain is 0.75, we will have 99% power to detect this difference.
 4. Aesthetic outcome of donor site on Vancouver Scar Scale
 - a. The Vancouver Scar Scale encompasses 4 separate outcomes to be objectively assessed. Each has been separately reported in the literature for each group in different papers as previously mentioned. We will compare the final score as well as scores within each outcome.
 - i. Vascularity (0-3): STSG group will likely average a 1, while Integra group will likely average around 0
 - ii. Pigmentation (0-2): STSG group will likely average a 1 while Integra group will likely average a 2
 - iii. Height (0-3): STSG group will be an average of about 1, while the Integra group will likely average a 0
 - iv. Pliability(1-5): We expect the STSG group to average about a 2, while the Integra group will average about a 1
 - v. Based on these scores, we would expect the STSG group to have a score of 5 while the Integra group will have an average score of about 3

We will compare these measures between the two groups using t-tests or Wilcoxon rank sum tests as appropriate. Assuming a standard deviation within each group of one and that data appears normal, we will have over 99% power to detect a difference of one and two scoring units for these tests.

5. Functional outcome as measured by pre and post-operative assessment on the QuickDASH (Disabilities of the Arm, Shoulder, and Hand) scale

The Use of Integra© in Coverage of Radial Forearm Free Flap Donor Site Defect

Comprehensive Cancer Center of Wake Forest University (CCCFWU)

CCCFWU # 99915A

- a. The survey asks the subject to rate the ease of 11 daily activities from 1-5, 1 being no difficulty, and 5 being unable to perform.
 - i. The scores are then averaged (Giving a score between 1 and 5), and one is subtracted from the average. This number is then multiplied by 25
 1. As the lowest possible rating on each activity is 1, this accomplishes bringing the lowest possible score to 0.
 2. As the highest possible rating on each activity is 5, this bring the highest possible score to be 100
 - ii. We will expect similar values as previously cited in the literature. About 70 for the subjects receiving a STSG, and values closer to 30 for the Integra group
 - iii. We will compare these two groups using t tests or Wilcoxon Rank Sum tests as appropriate. Assuming a standard deviation of 10 and that the data appears normal, we will have over 99% power to detect this difference using a two sample t test.
6. Functional outcome as measured by hand strength and Range of Motion
 - a. Range of motion will be measured by resident physicians taking part in the project who will be trained by the occupational therapy team at our institution. The measurements will be taken using electric goniometers so as to standardize the measurements as much as possible.
 - i. Previously reported differences in pre and postoperative range of motion of wrist flexion and extension have ranged from non-statistically significant to about 27 degrees and 22 degrees, respectively.¹
 1. We will expect the difference in wrist flexion and extension in the non-Integra group to be 25 degrees and 20 degrees, respectively.
 2. We will expect the difference in flexion and extension in the Integra group to be 15 and 10 degrees, respectively.[8]
 3. We will again employ two sample t-tests (or Wilcoxon Rank Sum Tests) to test for differences in these angle measurements. Assuming a common standard deviation of five degrees, we will have 99% power to detect a difference in five degrees using a two sample t test.
 - b. Hand strength will be measured by pinch and grip strength dynamometers obtained from the occupational therapy department at our institution. These measurements will be taken at 3 month, 6 month, and 1 year follow up clinic visits.
 - i. Grip strength has been reported to be about a 7kg difference between pre-operative and post-operative measurements, while Pinch strength has been shown to differ by approximately 0.75kg. [29]
 - ii. For the non-integra group, we predict a difference in grip strength of approximately 5kg, while the pinch strength will differ but about 0.75kg
 - iii. For the Integra group, we predict that the difference in grip strength will be approximately 3kg while the pinch strength will differ by approximately 0.25kg.
 - iv. At each time point, we will compare the hand strengths of the Integra and non-Integra groups using two sample t-tests or Wilcoxon Rank Sum Tests as appropriate. Assuming a 5kg grip strength standard deviation in each group, we will have over 99% power to detect differences of 5kg and 7 kg in each group.

The Use of Integra® in Coverage of Radial Forearm Free Flap Donor Site Defect

Comprehensive Cancer Center of Wake Forest University (CCCFWU)

CCCFWU # 99915A

- v. For pinch strength, we assume both groups have a standard deviation of 1kg. To detect a difference 0.75kg, we will have 95% power using a two sample t-test.

7. Wound Contracture and Skin Pliability

- a. We will use the same planimetry software to determine the percent of wound contracture.
 - i. Utilizing a dermal substitute, wound contracture has been shown to be as low as 15% of total area. We will expect the same amount from our study. [30]
 - ii. Wound contracture utilizing standard STSG has been shown in animal models to cause wound contracture of up to 38-41%. We will expect wound contracture of about 30% from our study. [31,32]
- b. Skin Pliability
 - i. We plan to use a Cutometer MPA 580 for measurements of skin pliability. We currently have this device on our budget for next year awaiting approval and are separately applying for a Plastic Surgery Foundation grant to fund these measurements.
 - ii. We plan to measure Pliability (Ua), Elasticity (Ue), Retraction (Ur), Viscoelasticity (Uv), and Extension (Uf)
 - 1. Previously measured values for these parameters in reconstruction utilizing Integra are as follows. [33]
 - a. $Ua = 0.083$ (0.192 Control)
 - b. $Ue = 0.088$ (0.153 Control)
 - c. $Ur = 0.037$ (0.086 Control)
 - d. $Uv = 0.039$ (0.068 Control)
 - e. $Uf = 0.098$ (0.221 Control)
 - f. Ur/Uf (Gross Elasticity) = 0.377
 - g. Ur/Ue (Elastic Function) = 0.125
 - h. Ua/Uf (Biological Elasticity) = 0.846
 - 2. Previously measured values for these parameters in STSG are reported as ratios and are listed here. [34]
 - a. Ur/Uf (Gross Elasticity) = 0.553
 - b. Ur/Ue (Elastic Function) = 0.818
 - c. Ua/Uf (Biological Elasticity) = 0.881
 - 3. For our study, we will expect the following parameters
 - a. Integra+STSG
 - i. $Ur/Uf = 0.4$
 - ii. $Ur/Ue = 0.1$
 - iii. $Ua/Uf = 0.8$
 - b. STSG
 - i. $Ur/Uf = 0.6$
 - ii. $Ur/Ue = 0.8$
 - iii. $Ua/Uf = 0.9$
 - iii. Should we not obtain funding for a cutometer, we will obtain measurements of maximal skin distension over the grafted area and compare it in a ratio to the maximal skin distension over the same area in the opposite arm.

The Use of Integra® in Coverage of Radial Forearm Free Flap Donor Site Defect

Comprehensive Cancer Center of Wake Forest University (CCCFWU)

CCCFWU # 99915A

1. In this manner, we would expect the Integra and STSG to give a ratio of about 0.75, while the STSG would give a ratio of about 0.4

References

1. Yang, G.F., et al., Forearm free skin flap transplantation: a report of 56 cases. 1981. *Br J Plast Surg*, 1997. 50(3): p. 162-5.

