1.1 Primary Objective(s)

Compare donor site aesthetic quality and functional outcomes of subjects with a classic STSG and those repaired with Integra and STSG.

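### Section 13.0 gives at least 16 tests (20 comparisons with repeat visits) a full two-sided 0.05 each, with no primary endpoint, primary time point or multiplicity rule

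*Combined protocol and SAP*

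**What the plan says.** Section 1.1 gives a single objective that spans two domains: "Compare donor site aesthetic quality and functional outcomes of subjects with a classic STSG and those repaired with Integra and STSG". It names no variable and no visit.

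Section 13.0 lists eight endpoints and calls none of them primary. The section uses the word only in the negative, in item 2c on graft necrosis: "this parameter is not a primary objective of the study but will be easy to measure". The endpoint list also says that "we will be focusing on the pliability aspect of the Vancouver Scar Scale", which signals emphasis but does not designate a primary.

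The error rate is set once for everything: "All hypothesis testing will two sided and performed at the 0.05 significance level". No hierarchy, adjustment or exploratory label follows. The sample size ("We plan to enroll 50 subjects in each group") is stated without saying which endpoint it was derived from. Because "No interim monitoring is planned for this study", the multiplicity comes only from endpoints and visits.

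Testing by visit is explicit only for grip and pinch: "At each time point, we will compare the hand strengths", with measurements at 3, 6 and 12 months. For the Vancouver scale, the Section 13.0 endpoint list has scores at 3, 6 and 12 months, whereas Section 5.0 adds the scale only at the 1-year visit.

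**The concern.** The plan implies a ranking of endpoints, since item 2c sets one parameter apart, but never writes that ranking down. Any of the tests could therefore be presented as the main finding once the results are known.

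The endpoints can also disagree, and the plan expects some to. In item 4 the predicted pigmentation score is higher with Integra (2 against 1), while the predicted total is lower (3 against 5). With no designated primary, nothing fixes in advance which single result settles the objective or at which visit. The nominal 5% would then not describe the error rate of whatever claim is made.

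**Working it through.** **1. Reproduce the plan's own power.** Item 1 states 81% power for tendon exposure, 25% against 5%, with 50 per group. The chi-squared test with pooled variance under the null and two-sided 0.05 gives:

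- null standard error = √(2 × 0.15 × 0.85 / 50) = 0.0714
- alternative standard error = √((0.25 × 0.75 + 0.05 × 0.95) / 50) = 0.0686
- power = Φ((0.20 − 1.960 × 0.0714) / 0.0686) = Φ(0.876) = 0.809

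This matches 81%. The same formula gives 0.624, 0.155, 0.286 and 0.388 for necrosis rate, necrosis percent, pain and paresthesia (stated: 62%, 16%, 29% and 39%). The stated chi-squared powers therefore all rest on an unadjusted 0.05.

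**2. Count the tests in Section 13.0, Statistical Analysis.**

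| Item | Tests | Number |
|---|---|---|
| 1 | tendon exposure | 1 |
| 2 | necrosis rate, necrosis percent | 2 |
| 3 | pain, paresthesia, pain severity | 3 |
| 4 | Vancouver total and four sub-scores | 5 |
| 5 | QuickDASH | 1 |
| 6a | wrist flexion, wrist extension | 2 |
| 6b | grip, pinch | 2 |
| | **Total** | **16** |

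Grip and pinch at three visits add 2 × 2 = 4, making 20 comparisons. Item 7 (contracture, skin pliability) gives expected values but no test, so it is left out. That is why 16 is a minimum.

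**3. Chance of at least one false positive, assuming no true difference on any endpoint.** For k independent tests, the chance in either direction is 1 − 0.95^k. The chance of at least one false result favouring Integra is 1 − 0.975^k, because a two-sided 0.05 test puts 0.025 on each side. For correlated tests, normal test statistics with equal pairwise correlation were simulated. The correlations are assumptions.

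| | Independent | Correlation 0.3 | Correlation 0.5 |
|---|---|---|---|
| 16 tests, either direction | 56% | 48% | 37% |
| 20 comparisons, either direction | 64% | 54% | 42% |
| 16 tests, favouring Integra | 33% | 24% | 19% |
| 20 comparisons, favouring Integra | 40% | 28% | 21% |

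The expected number of false positives is 16 × 0.05 = 0.8 or 20 × 0.05 = 1.0, whatever the correlation.

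**4. Check with a less uniform structure.** A second simulation makes the Vancouver total the sum of its four sub-scores. It assumes correlation 0.3-0.7 within domains, 0-0.3 between domains and 0.7-0.9 between visits. The either-direction chance is 40-53% for 16 tests and 44-58% for 20 comparisons, inside the ranges above.

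**5. Cost of adjusting every test instead.** Bonferroni over 16 tests gives 0.05 / 16 = 0.003125 each. Power for tendon exposure falls from 81% to 44%, for necrosis rate from 62% to 24%, and for a 0.75 kg pinch difference from 96% (recomputed; the plan states 95%) to 79%.

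**The case against.** The best defence is that the plan is less open than it looks. Section 1.1 speaks of aesthetic and functional outcomes, and Section 13.0 uses those words to head item 4 (Vancouver), item 5 (QuickDASH) and item 6 (strength and range of motion). Pliability is also singled out. On that reading only 5 + 1 + 4 = 10 of the 16 tests bear on the objective. This narrows the field but does not settle it: for 10 tests at one time point the chance of any false positive is still 1 − 0.95^10 = 40% if independent, and 29% at correlation 0.5. No one of the ten is put first.

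Three stronger readings are tempting, and the documents do not support them.

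- *A chance significant result is more likely than not.* For 16 tests this needs near-independence. Exact independence is impossible, because all tests use the same 100 subjects and the Vancouver total is tested alongside its own components. At equal correlation the figure is 52% at 0.2 and 48% at 0.3. For 20 comparisons it passes below 50% between 0.3 and 0.4.
- *An ineffective treatment would probably be reported as beneficial.* Testing is two-sided, so half of chance findings favour the plain graft. The chance of a false result favouring Integra stays at or below 40% across the stated comparisons. Nor does the plan contain a trial-level rule that any one significant test means success; the 0.05 is a per-test level.
- *Every endpoint is tested at three visits (48 tests).* Only hand strength is tested at each visit. The conflicting Vancouver schedules need reconciling, but they are not evidence of 48 tests.

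**Conclusion.** The point stands and should be fixed before analysis. Following Section 13.0 as written carries roughly a 37-56% (16 tests) or 42-64% (20 comparisons) chance of at least one false positive in either direction. Under the correlations examined, that is about 7 to 13 times the nominal 5% (37 / 5 = 7.4; 64 / 5 = 12.8). These figures assume no true difference on any endpoint and a pairwise correlation between 0 and 0.5, which the documents do not supply. The absence of a primary endpoint, primary visit and multiplicity rule is read directly from the text and depends on none of these assumptions. As it stands, the plan cannot support a confirmatory claim from any single comparison.

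**What to change.** Before any unblinded analysis, amend Section 13.0 to name one primary endpoint at one visit, tested at two-sided 0.05 and tied to Section 1.1. The choice is the sponsor's.

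- **An option that fits the objective as written:** the Vancouver total at 12 months, rated by the blinded co-investigator, followed in fixed order by QuickDASH at 12 months, also at 0.05. Twelve months is the one visit at which Sections 5.0 and 13.0 agree that the Vancouver scale is scored. The plan states over 99% power for both under its own assumptions.
- **If tendon exposure is preferred:** it keeps its stated 81% power at 0.05. However, the graft site is evaluated for tendon exposure at 3, 6 and 12 months, so the assessment window must be defined. Section 1.1 must also be aligned, because the plan labels tendon exposure neither aesthetic nor functional.

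Report all other endpoints and visits, including those at 3 and 6 months, as secondary estimates with confidence intervals and no confirmatory claim. Reconcile the two Vancouver schedules in the same amendment.

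The cost is wording only: no extra subjects or assessments, and the primary test keeps its full 0.05. The downside is that the remaining endpoints lose confirmatory status, and any endpoint later in the fixed order loses it if an earlier test fails.
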